6.1.2 Incontinence-Related Quality of Life

To address incontinence-related quality of life, participants will complete the following validated questionnaire measures at baseline, 6 weeks, and 12 weeks, as well as 12 and 24 weeks after the end of the yoga and stretching/strengthening control programs:

- A. Incontinence Impact Questionnaire (IIQ)-- a validated, 28-item measure of the impact of incontinence on 4 domains of functioning and quality of life (physical activity, emotional health, relationships, and travel).^{48,49} Scores range from 0 to 100; higher scores indicate worse impact.
- B. Urogenital Distress Inventory-6 (UDI-6)-- a validated, 6-item measure that assesses subjective distress from frequent urination, urgency incontinence, stress incontinence, small-volume leakage, difficulty emptying the bladder, and genital pain.⁴⁹ Scores are scaled from 0 to 100.
- C. Patient Perception of Bladder Condition (PPBC)-- a validated single-item measure assessing the degree to which respondents consider their condition to be a problem on a 6-point scale.^{50,51}
- D. Pelvic Organ Prolapse/Incontinence Sexual Questionnaire, IUGA-Revised (PISQ-IR)- a validated 20-item measure of sexual function in women with pelvic floor disorders (PFDs), designed to be appropriate for both sexually active and inactive women.⁵²

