9.2 Sample Size

Sample size has been calculated based on parameter estimates derived from both the investigators' past pilot studies on yoga as well as other group-based incontinence intervention trials conducted by study team members.¹⁰³ Assumptions include: a) average baseline frequency of incontinence of ~23-24 episodes/week; b) standard deviation (SD) of change in incontinence frequency of ~14.4; c) correlation between outcome values of ~0.59; and d) loss of ~15% by 3 months. Assuming a ~50% decrease in incontinence frequency among controls (which is the threshold at which women with daily incontinence start to perceive meaningful benefit from treatment¹⁸), the team will power the study to detect a between-group difference in reduction in incontinence of at least 20% in the yoga versus stretching/strengthening control group (corresponding to a \geq 70% reduction in frequency of incontinence in the yoga group) at 3 months. Under these assumptions, a sample size of 240 (120 per group) will provide 80% power in 2-sided tests with 5% type-I error to detect a between-group difference in reduction in the primary outcome of total incontinence frequency of at least 20% in the yoga vs. control arm. With regard to secondary outcomes, this sample will also provide 80% power to detect moderate between-group differences of 0.26 to 0.39 SDs, assuming intraclass correlation of outcomes in the range of 0.4-0.8.

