Planned analyses: Additional LMMs will examine other secondary outcomes including incontinence-related quality of life as assessed by validated questionnaires (i.e., the Incontinence Impact Questionnaire (IIQ), Urogenital Distress Inventory (UDI), Patient Perception of Bladder Condition (PPBC), Pelvic Organ Prolapse/Incontinence Sexual Questionnaire, and IUGA-Revised (PISQ-IR) questionnaire), as well as depression and anxiety symptoms assessed by additional questionnaires (i.e., the Center for Epidemiology Studies Depression Scale (CES-D), Hospital and Anxiety Depression Scale (HADS), and State Trait Anxiety Inventory (STAI)). We will again estimate intention-to-treat intervention effects, adjusting for study location, using the same modeling strategy as for objective 1. Transformation or categorization of questionnaire scores (in combination with logistic or proportional odds models) will be considered as needed to deal with skewness of outcomes.

Objective 4: To explore whether the yoga intervention is associated with improvements in 1) pelvic floor muscle strength, 2) peripheral autonomic function, and/or 3) lower extremity physical function, and assess whether improvements in these factors may mediate improvement in incontinence.

Hypothesis 4A: Among ambulatory incontinent women enrolled in this trial, the yoga intervention will be associated with improvements in a) pelvic floor muscle strength (assessed by pelvic exam), b) cardiac autonomic function (assessed by heart rate variability and impedance cardiography), and c) lower extremity physical function (assessed by physical performance assessment) over 12 weeks.

Hypothesis 4B: Among ambulatory incontinent women enrolled in this trial, changes in incontinence frequency over 12 weeks will be partly mediated by changes in a) pelvic floor muscle strength, b) cardiac autonomic function, and c) lower extremity physical function.

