Planned analyses: Additional intermediary outcomes include pelvic floor muscle strength (measured by Brink scale), peripheral autonomic function (reflected by respiratory sinus arrhythmia [RSA] and cardiac pre-ejection period [PEP] parameters), and lower extremity physical function (assessed using the Short Physical Performance Battery [SBBP] and 2-minute step test). Intervention effects will first be estimated using LMMs, using the same modeling strategy used for objectives 1-3. Next, to assess for mediation of changes in incontinence frequency by changes in these factors, we will assess correlation between changes in these

parameters and change in incontinence frequency between baseline and 12 weeks. We will then examine attenuation of intervention effects estimates from the primary intention-to-treat analyses after adjustment for these potential mediators. Mediators will initially be analyzed as continuous variables (i.e., continuous change in RSA and PEP), but categorization will be considered in the event of skewed variable distributions. If evidence of mediation is observed, we will estimate 95% bias-corrected percentile confidence intervals for the proportion of intervention effect explained, using resampling by participant to fully account for the correlation between intervention effect estimates before and after adjustment for change in the mediators

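### Categorisation is the only remedy named for skewed mediators in Objective 4; it would usually understate the proportion explained, and a spline avoids this

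*Combined protocol and SAP*

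**What the plan says.** All of this is in the combined protocol and SAP, section 9.6.1, planned analyses for Objective 4.

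- The objective is exploratory: "To explore whether the yoga intervention is associated with improvements in 1) pelvic floor muscle strength", with autonomic and lower-extremity function alongside.
- Mediation is judged by attenuation: "We will then examine attenuation of intervention effects estimates from the primary intention-to-treat analyses after adjustment for these potential mediators". If mediation is seen, the proportion of the effect explained is reported with a 95% bias-corrected percentile bootstrap interval, resampling participants.
- The default form is continuous: "Mediators will initially be analyzed as continuous variables". The examples given are change in RSA and change in PEP.
- The contingency for skewness is that "categorization will be considered in the event of skewed variable distributions".

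The plan gives no skewness threshold, number of groups, cut-points or time by which the choice is made. Neither transformation nor a flexible continuous form is mentioned for mediators.

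**The concern.** In the attenuation step the mediator is on the right-hand side of the model. Linear and mixed models make assumptions about residuals and about the form of the relation, but none about the distribution of a covariate. A skewed mediator can bring high-leverage points or a curved relation with the outcome. Both are reasons to model the relation flexibly, not to cut the variable.

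Cutting has a predictable cost. Women in the same category still differ in the mediator, and if yoga shifts it, part of that shift occurs within categories. Adjusting for category membership cannot remove that part, so it stays in the adjusted treatment effect and the proportion explained comes out too small. The planned bootstrap interval would not show this: its bias correction concerns the resampling distribution of the estimator, and the interval would be placed around the attenuated value.

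At stake is the reported answer to Hypothesis 4B, how much of the effect runs through pelvic floor strength, autonomic function or physical function. With cut-points left open, that answer would also depend on a choice made after the distributions are seen.

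**Working it through.** The plan states no figure for what categorisation costs, so there is none to reproduce.

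**Assumptions, none from the documents.** The outcome is linear in the mediator. The mediator is normal within arm with SD 1. There is no mediator-outcome confounding or measurement error. Groups are of equal size. The true proportion explained is P = 0.50.

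**Formula.** Let a be the treatment effect on the mediator, b the slope of the outcome on the mediator and c the remaining treatment effect, so P = ab/(c + ab). Divide the mediator into k groups with shares p_j and group means m_j. The share of mediator variance that the groups capture is R_k = sum of p_j × m_j². For a modest a, the treatment effect adjusted for the groups is about c + ab(1 − R_k), so the reported proportion is about P × R_k.

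**Numbers.**

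- Two groups: the group means are ±√(2/π) = ±0.798, so R = 2/π = 0.637 and 0.50 × 0.637 = 0.318.
- Three groups: the outer means are ±1.091 and the middle mean is 0, so R = (2/3) × 1.091² = 0.793 and 0.50 × 0.793 = 0.397.
- Four groups: R = 0.861 and 0.50 × 0.861 = 0.431.
- Five groups: R = 0.897 and 0.50 × 0.897 = 0.449.

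Simulation of the linear model with 2,000,000 records and treatment effects on the mediator of 0.3 to 0.8 SD agrees: 0.32, 0.40, 0.43–0.44 and 0.45. The continuous mediator leaves about 0% of the mediated effect behind.

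**Skewed mediators.** The contingency applies when the mediator is skewed, so the check was repeated with a lognormal mediator (log-SD 1), true proportion again 0.50:

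| Mediator entered as | Outcome linear in the mediator | Outcome linear in its log |
|---|---|---|
| Raw, linear term | 0.51 | 0.27 |
| Two groups | 0.28 | 0.32 |
| Three groups | 0.36 | 0.40 |
| Four groups | 0.40 | 0.44 |
| Five groups | 0.42 | 0.46 |
| Log | 0.52 | 0.50 |

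In a further set of shapes, two groups gave 0.27–0.34, three gave 0.35–0.41 and five gave 0.41–0.46. A spline on the continuous mediator gave 0.49–0.50 in every shape in that set.

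**The case against.** Four points on the other side have weight.

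1. Categorisation is a contingency. Mediators are continuous first, cutting is only to be considered, and the objective is exploratory. The primary linear mixed model has no such option. This stands and limits the importance of the point.

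2. Leaving a skewed mediator as a raw linear term can be worse than cutting it: 0.27 against 0.32 or more when the outcome follows the log of the mediator. This also stands. It means that deleting the contingency is not enough, but it does not favour categories, because the spline recovers the true value in both columns of the table.

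3. The usual alternatives have faults. The mediators are change scores, which can be zero or negative, so a plain log is undefined. A rank transformation reported 0.65 for a true 0.50 with a skewed change score. Both are therefore left out of the fix. Change in the Brink score (section 6.1.7, range 0 to 12) is already coarse, so a spline adds little there.

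4. The sentence may also be meant for the preceding step, where the mediators are outcomes and skewed residuals can matter. The point here concerns only their use as covariates.

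A reader might infer more than the documents support. One inference is that a third or more of the information is lost. That is true of a two-group split of a normal variable (36.3%), but the plan does not say two groups, and three, four or five groups lose about 21%, 14% and 10%.

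Another inference is that the Objective 3 questionnaires share the defect and that power would fall from 80% to 61%. There the plan says "Transformation or categorization of questionnaire scores (in combination with logistic or proportional odds models) will be considered as needed to deal with skewness of outcomes". Transformation is already listed, and proportional odds models imply three or more categories. The PPBC, a "single-item measure assessing the degree to which respondents consider their condition to be a problem on a 6-point scale", is ordinal to begin with. The 61% again assumes a median split of a normal score. For lognormal scores with log-SD 0.5, 0.75 and 1.0, a median split has 0.723, 0.855 and 1.094 times the efficiency of a raw-scale mean comparison. Under strong skewness the choice is a trade-off, not an error.

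**Conclusion.** The point holds for mediators only. Section 9.6.1 names one response to skewness, and it answers a requirement that the attenuation model does not have. Under a linear model with a normal mediator and equal groups, a true proportion explained of 0.50 would be reported as about 0.32, 0.40, 0.43 or 0.45 with two, three, four or five groups. That is an understatement of about 0.18 down to 0.05.

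The size depends on the number of groups and the shape, neither of which the plan gives. The downward direction holds in the shapes tabulated above but is not a theorem: for an extremely skewed change score that treatment shifts as a whole, coarse groups can err the other way. Neither direction argues for cutting.

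The consequence is confined to Hypothesis 4B in the exploratory objective. The primary analysis and the questionnaire outcomes are untouched. This is a minor improvement, worth making because it is nearly free.

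**What to change.** In section 9.6.1, planned analyses for Objective 4, replace the clause on categorising skewed mediators with wording such as: *mediators will be kept continuous; if skewed or non-linearly related to the outcome, they will be entered as a restricted cubic spline with knots fixed at pre-specified quantiles*.

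State the number of knots and their quantiles before the 12-week unblinding described in section 9.3. For coarse measures such as change in the Brink score, where quantile knots may coincide, state in advance that fewer knots or a linear term will be used. Do not substitute a plain log. The bootstrap for the proportion explained can stay as planned, with the spline terms refitted in each resample.

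The cost is one sentence, a few extra model terms, and a mediator relation that has to be shown as a curve because a single coefficient no longer describes it. No new data or participants are needed, and the questionnaire sentence under Objective 3 need not change for this reason.

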6.1.6 Cardiac Autonomic Function Measures

To guide exploration of changes in autonomic nervous system function as a potential mediator of intervention effects in women with incontinence, participants will undergo the following measures at baseline and 12 weeks. During the COVID-19 pandemic, participants may decline to undergo these measurements that require them to come into close proximity (less than 6 foot distance) with study personnel.

- A. High frequency heart rate variability (a.k.a. respiratory sinus arrhythmia, or RSA) refers to the degree to which heart rate accelerates and decelerates during the respiratory cycle, and has been shown to be a reliable marker of cardiac parasympathetic activity.⁷¹⁻⁷³ Evaluation of rest-to-stress changes in RSA allows for assessment of abnormalities in adaptive vagal regulation, previously shown to be associated with bladder instability and urine leakage in response to stressful events.²⁰⁻²² Procedures for assessing RSA, monitoring data quality, and interpreting findings have been designed by co-investigator [name], who has authored one of the main textbooks on autonomic assessment,⁷⁴ published four methodological articles and chapters on this topic,⁷⁵⁻⁷⁸ and collaborated with the research team on other NIH-funded studies.⁷⁹ Heart rate variability measurements will be obtained according to standard protocols from the North American Society of Pacing & Electrophysiology,⁸⁰ in which two ECG electrodes will be attached to each participant's right and left wrists using pre-gelled sensors while in the seated position. Following an initial 10-minute "resting" recording, a 10-minute "stress" recording will be obtained while the participant completes two stress tasks, including a visual attention and tracking task⁸¹ shown to reliably induce vagal

withdrawal in subjects across the lifespan.^{75,76} Analyses using Mindware software will examine both resting and rest-to-stress change in RSA.

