B. Systolic pre-ejection period (i.e., PEP, the time period between the left ventricle contracting and the aortic valve opening) will be examined as an established measure of sympathetic activity that can be measured non-invasively using impedance cardiography.^{72,73} For this study, PEP will be measured using the impedance cardiography module of the same Biopac MP100 system used to assess RSA above. According to established protocols⁸² also used in other NIH-funded studies by the team,⁷⁹ a standard tetrapolar band electrode system will be attached to each participant while in the seated position (two inner electrodes placed at the xiphisternal joint and the base of the neck, outer electrodes placed 3 cm distally to the inner electrodes) and connected to the impedance cardiograph module. Impedance cardiogram recordings will be obtained over the same time interval as RSA recordings, including a resting period and a stress period. This will include a computer-based stress task designed by co-investigator [name] to assess sympathetic reactivity,⁸³ which participants must complete with limited instruction and under time constraints. Analyses using Mindware software will examine both resting and rest-to-stress change in PEP.

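### The only planned mediation interval depends on an undefined finding of evidence of mediation, so Hypothesis 4B is reported selectively and cannot be answered negatively with stated precision

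*Combined protocol and SAP*

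**What the plan says.** The planned analyses for Objective 4 (Section 9.6.1) run in order. Linear mixed models first estimate yoga's effect on each intermediary measure: the Brink score, RSA and PEP parameters, the Short Physical Performance Battery and the 2-minute step test. Changes in these measures are then correlated with change in incontinence frequency. Next comes attenuation: "We will then examine attenuation of intervention effects estimates from the primary intention-to-treat analyses after adjustment for these potential mediators". Last comes the conditional step: "If evidence of mediation is observed, we will estimate 95% bias-corrected percentile confidence intervals for the proportion of intervention effect explained".

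No attenuation cut-off, significance level, multiplicity rule or adjustment set is given. Other conditional analyses in Section 9.6.2 do have criteria: subgroup effects are shown only if the interaction reaches p < 0.05, and the length-of-exposure analysis follows a closed procedure at alpha 0.05.

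Section 6.1.6 takes each autonomic measure in two forms: "Analyses using Mindware software will examine both resting and rest-to-stress change in RSA" and "Analyses using Mindware software will examine both resting and rest-to-stress change in PEP".

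**The concern.** The judgement that mediation is present comes before any interval for mediation exists. It decides which mediators receive one. The correlation and attenuation steps do not need yoga to have moved the mediator. A factor that tracks incontinence in both arms will correlate with it, and a chance imbalance between arms can then produce attenuation. The mixed model for the mediator would inform the judgement, but the plan does not make a non-zero effect there a requirement.

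Two things are at stake. The proportions explained that carry an interval will be a selected set, chosen by a rule that can be settled after the data are seen. Mediators judged to show no evidence get no mediation interval, so the report cannot say how large a pathway remains compatible with the data. Because the only planned interval is for a ratio, no absolute indirect effect is reported for any mediator.

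**Working it through.** **Inputs from Section 9.2.** "a sample size of 240 (120 per group) will provide 80% power in 2-sided tests with 5% type-I error"; "average baseline frequency of incontinence of ~23-24 episodes/week"; "standard deviation (SD) of change in incontinence frequency of ~14.4"; "correlation between outcome values of ~0.59"; a 20-point difference in percent reduction; 15% loss by 3 months.

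**1. The plan's own figure.** Residual SD = 14.4 × √(1 − 0.59²) = 11.63. Effect at a baseline of 23 = 0.20 × 23 = 4.6 episodes/week. n per arm = 2 × (1.96 + 0.84)² × 11.63² / 4.6² ≈ 100, or 101 with the small-sample correction. 101 / 0.85 gives 119 per arm, 238 in total, against 240 stated. Power with 240 × 0.85 / 2 = 102 per arm is 0.807. Baselines of 23.5 and 24 give totals of 230 and 220. The sample size is not at issue here. It fixes the simulation setting: 102 per arm, residual SD 11.63, effect 0.20 × 23.5 = 4.7.

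**2. Number of mediators.** Objective 4 names five measures. Splitting RSA and PEP into resting and rest-to-stress forms gives seven. Leaving out the Short Physical Performance Battery, which Section 6.1.5 does not list, gives six. The range used is 5-7.

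**3. Loosest reading, by formula.** In a linear model, the unadjusted minus the adjusted intervention coefficient equals a × b, where a is the arm difference in the mediator and b the mediator's slope on the outcome. If yoga does not move the mediator, a is centred on zero and the product is positive half the time. For k independent mediators, P(at least one positive) = 1 − 0.5^k: 96.9% (k = 5), 98.4% (k = 6), 99.2% (k = 7).

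**4. Other readings, by simulation.** 6,000 trials per setting, with yoga's effect on every mediator set to zero. Assumed, because the documents give no values: inter-mediator correlation 0-0.6 and mediator-outcome correlation 0-0.3. Chance that the criterion is met by at least one mediator (or, for joint adjustment, by the single joint model):

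- any positive attenuation, one mediator at a time: 97-99% if independent, 90-98% at inter-mediator correlation 0.3, 80-94% at 0.6
- positive attenuation plus a correlation with p < 0.05: 12-99%
- attenuation of at least 10%, one at a time: 3-73%
- attenuation of at least 20%, one at a time: 1-21%
- joint adjustment, any attenuation: about 50%
- joint adjustment, attenuation of at least 10%: 5-35%
- positive attenuation plus a significant yoga effect on the mediator: 8-17%
- both paths significant, with attenuation: 0.5-16%

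The top of the last range agrees with a direct calculation. If the mediator-outcome path is always detected, each null mediator passes with probability 0.05 / 2, and 1 − 0.975⁷ = 16.2%.

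**5. What the condition does to the intervals.** Bias-corrected percentile intervals for the proportion explained were simulated for six null mediators (600 trials, 1,000 resamples each; mediator-outcome correlation 0.1 and 0.3, inter-mediator correlation 0 and 0.3). The lower limit exceeded zero for 1.0-3.9% of mediators. About half of all mediators pass a positive-attenuation criterion, so among the intervals reported the rate is 2.0-7.8% (for example 0.0386 / 0.496 = 0.078). At least one of the six had a lower limit above zero in 5-20% of trials. That count is the same with or without the criterion, because every such interval also had positive attenuation.

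**The case against.** A reader might infer that evidence of mediation is to be judged from point attenuation alone, so that a trial in which yoga moves no mediator would almost surely report mediation. The documents do not support this. Section 9.6.1 puts the mixed model for each mediator first, which is Hypothesis 4A, and Objective 4 speaks of improvements in these factors as what may mediate. An analyst who used that step as a filter would be in the 0.5-17% range. The wording also permits joint adjustment, where the figure is about 50% or less.

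It is also fair to say that passing the condition only triggers an interval, so a spurious pass has its uncertainty shown, and for a null mediator that interval usually includes zero. True mediators would pass too. The correlations are assumptions. Objective 4 is exploratory, carries no alpha, and does not touch the primary or secondary efficacy analyses.

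All of this stands, and it limits the size of the problem. None of it supplies the missing criterion or adjustment set, or gives an interval to the mediators that fail.

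**Conclusion.** The point holds as one of an undefined condition and selective reporting. Depending on a choice the plan leaves open, the chance that at least one null mediator passes runs from about 0.5% to 99%. The 80-99% figure belongs only to the loosest reading: any positive attenuation, one mediator at a time. It should not be quoted as a property of the plan. Nor does the condition produce additional intervals that exclude zero. It concentrates them, roughly doubling their rate among those reported.

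The firmer consequence needs no simulation: mediators that fail the condition have an estimate of yoga's effect on them but no interval for mediation, so Hypothesis 4B cannot be answered negatively with stated precision. The numbers rest on 102 analysed per arm, a linear model, five to seven mediators and assumed correlations. Fewer women may contribute, since the pelvic exam is optional (Section 6.1.7) and the autonomic measures could be declined during the pandemic (Section 6.1.6). The change is worth making because it is cheap, but it concerns an exploratory objective.

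**What to change.** Delete the condition on evidence of mediation and specify the following.

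- Enter each listed mediator one at a time, with one joint model as a supplement. List the mediators, including which RSA and PEP forms count.
- For every mediator, report yoga's effect on it and the indirect effect in episodes per week (unadjusted minus adjusted intervention coefficient, same participants in both models), each with a participant-level bootstrap 95% CI.
- Describe a factor as a possible mediator only if its indirect-effect CI excludes zero in the direction of benefit and the CI for yoga's effect on that factor also excludes zero.
- Label this exploratory, name the interval type, and state how many mediators were examined. Per-mediator 95% intervals do not control error across mediators, and bias-corrected ones need particular care: in a small check (200 trials per setting, six null mediators), two-sided bias-corrected intervals for the indirect effect excluded zero for at least one mediator in about 12-38% of trials.
- Give the proportion explained only as a secondary description, when the CI of the intention-to-treat effect excludes zero.

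The cost is SAP wording and a few extra bootstrap runs. The downside is wide intervals that must be shown and fewer positive statements about mediation.
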